5. Known to be living with HIV (i.e., enrolled in a treatment program), or consent to HIV testing to confirm HIV status.

VI.D.2. Exclusion Criteria

1. Have positive pregnancy test or report to be pregnant at the time of visit or less than 6 weeks post-partum (will be asked to make an appointment 6 or more weeks post-partum)
2. Report to be menstruating at the time of visit (will be asked to make new appointment)
3. History of hysterectomy and no longer have a cervix
4. History of treatment for cervical abnormalities after cervical screening
5. History of cervical cancer
6. Report no previous sexual activity
7. Because this study has age-specific enrollment goals for WLWH and HIV[-] women, once those enrollment goals are met for each study group, the respective cohorts will be closed and other eligible women will be excluded.

VI.E. Recruitment and Eligibility Screener

During the period of recruitment at a health clinic, WLWH and HIV[-] women will be solicited using advertisements throughout the entire clinic as well as outreach using community health workers (**Figure 1**). In addition, WLWH who are attending routine appointments at the HIV clinics will learn about the study during the group study overview sessions held in the health education room. All women who are interested in the study will meet with a study nurse who will give them an informational flyer and provide a brief verbal description of the study. The

study nurse will help the woman complete the eligibility screener that includes criteria listed above. If eligible and interested, the woman will register for an enrollment visit.

[figure not shown]

Figure 1. Participant recruitment

VI.F. Study Visits

VI.F.1. Enrollment Visit

VI.F.1.a. Informed Consent, HIV testing and Study Questionnaire

As outlined in **Figure 2**, at the enrollment visit conducted in a private exam room, the study nurse will describe the details of the study verbally and women will be provided an opportunity to ask any questions. The participant eligibility will be verified using the eligibility form. Women who report menstruating at the time of visit will be asked to make a new appointment 2 weeks later. Women who report to be pregnant or less than 6 weeks post-partum will be asked to make an appointment 6 or more weeks post-partum.

[figure not shown]

Figure 2. Enrollment visit procedures

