Women will individually undergo the consenting process as described in **Section X.B.1**. Once the Informed Consent Form (**Appendix II**) is completed, a unique study participant

identification number (PID) will be assigned to the participant that will be used to identify all forms and specimens collected at the enrollment and follow-up visits.

Participants' personal contact information will be confirmed. Participants will provide a urine sample for pregnancy testing to confirm they are not pregnant. Counseling will be provided pre and post testing as needed. Participants who are not known to be living with HIV will have a rapid HIV test with pre- and post-HIV-testing counseling following the National Rapid HIV Diagnostic Testing Protocol. Any participant who tests positive will be referred to the health center's HIV clinic for HIV management following the Ministry of Health's HIV management guidelines. The consent form obtains the participants' permission to extract from medical records information related to their HIV care including CD4 count, viral load, ART use and age of initiation of HIV care. They will then complete a short questionnaire on socio-demographic information and risk factors for HPV including sexual behaviors (**Appendix III**). The questionnaire will be conducted in private, using an automated audio interview assistance tool Audio Computer-Assisted Self-Interview (ACASI) software. The study nurse will provide additional assistance only if requested.

VI.F.1.b. Blood Collection

For the study of anti-HPV16 and HPV18 antibody titers between WLWH and HIV[-] women (Specific Aim 2 listed above), the study nurse will collect one 5 mL tube of blood from all participants for HPV antibody serology testing.

VI.F.1.c. Cervicovaginal, Anal, and Oral Specimens

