Notably, the study groups of participants are fundamentally different populations (vs. a randomized control trial that would recruit from the same population and, as result of randomization, enroll similar, representative populations in each arm). Specifically, there are known differences in age (and therefore possible differences sexual behaviors) between Gardasil®-vaccinated vs. -unvaccinated WLWH, and possible differences in sexual behaviors between Gardasil®-vaccinated WLWH vs. HIV[-] women (since HIV infection predominately is sexually transmitted in this population). Therefore, we will use a relative measure of effectiveness to account for the differences in age and possible differences in exposure to HPV. We will use logistic regression to calculate the odds ratio (OR) of the point prevalence and the prevalence of persisting HPV infections of Gardasil®-targeted HPV types, individually (HPV6, 11, 16, or 18) and in aggregate (HPV6, 11, 16, and 18), vs. untargeted HPV genotypes for which there is no evidence of cross-protection, for each anatomic site individually (cervix, anus, OR oral cavity) and combined (cervix, anus, AND oral cavity). That is, we will compare the ratio between study groups of participants as follows:

$\frac{N_{HPV6/11/16/18}}{N_{HPV35/39/51/52/53/56/58/59/66/68}}$ [vaccinated WLWH] (Group 1)
 $\frac{N_{HPV6/11/16/18}}{N_{HPV35/39/51/52/53/56/58/59/66/68}}$ [unvaccinated WLWH] (Group 2)
 or

$\frac{N_{HPV6/11/16/18}}{N_{HPV35/39/51/52/53/56/58/59/66/68}}$ [vaccinated WLWH] (Group 1)
 $\frac{N_{HPV6/11/16/18}}{N_{HPV35/39/51/52/53/56/58/59/66/68}}$ [vaccinated HIV[-] women] (Group 3)

or

$\frac{N_{HPV6/11/16/18}}{N_{HPV35/39/51/52/53/56/58/59/66/68}}$ [vaccinated HIV[-] women] (Group 3)
 $\frac{N_{HPV6/11/16/18}}{N_{HPV35/39/51/52/53/56/58/59/66/68}}$ [unvaccinated HIV[-] women] (Group 4)

This will allow us to account for differences in HPV exposure, prevalence, and persistence due to differences in age (n.b., prevalence equals incidence * duration; prevalent infections at older ages tend to be more persistent ((108)) and sexual behaviors between groups. Additional logistic regression models may be used to adjust specifically on other factors, including age, number of doses, and sexual behaviors, to account for population differences between study groups.

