Sample size calculation relates to the relative effectiveness measure as discussed. Under above assumptions, a sample size of 757 vaccinated and 757 unvaccinated WLWH will provide $\geq 80\%$ power ($p=0.05$) to detect an OR of ≤ 0.5 for 6-12 month persistent HPV6/11/16/18 infections, relative to HPV35/39/51/52/53/56/58/59/66/68 (but not HPV31/33/45 because of possible cross protection), in Gardasil®-vaccinated vs. -unvaccinated WLWH. Consequently, because there will be more participants with a prevalent infection than 6-12 month persistent HPV infection (because there are no losses to follow-up or HPV viral clearance for which to account), there will

be $\geq 80\%$ power ($p=0.05$) to detect a OR of ≤ 0.75 in point prevalence of HPV6/11/16/18 infection relative to HPV35/39/51/52/53/56/58/59/66/68, in Gardasil®-vaccinated vs. - unvaccinated WLWH.

VII.B. Specific Aim 2

To quantify, and examine the determinants of, long-term antibody responses to, HPV vaccination.

VII.B.1. Analyses.

Geometric mean titers (GMT) and seropositivity (seroconversion) will be compared between 1) HPV-vaccinated WLWH and HPV-vaccinated HIV[-] women, overall and stratified on the number of vaccine doses, 2) HPV-vaccinated and unvaccinated WLWH, overall and by the number of doses received by the HPV-vaccinated WLWH, and 3) three vs. two doses for HPV-vaccinated WLWH and 4) HPV-vaccinated and unvaccinated HIV[-] women, overall and by the number of doses received by the HPV-vaccinated HIV[-] women.

Differences in GMT and seropositivity will be tested for statistical significance using the Mann-Whitney and Fisher's exact tests, respectively. ANOVA and logistic regression models will be used to adjust for/assess the association of other factors (e.g., age at vaccination, age at enrollment into the study, number of doses, HIV status [positive vs. negative and current antiretroviral therapy, CD4 counts, and HIV viral load] and history [e.g., CD4 nadir], and detection of HPV genotypes, etc.) with GMT and seropositivity, respectively.

Among vaccinated and unvaccinated HPV seropositive WLWH, the association between HPV antibody titer and presumed route of HIV acquisition (either maternal to child or behavioral) will be examined.

VII.B.2 Sample Size/Power to compare Gardasil®-vaccinated WLWH vs. Gardasil®-vaccinated HIV[-] women.

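### Aim 2 treats seropositivity in one enrollment sample as seroconversion to vaccine, so the contrast of vaccinated WLWH with vaccinated HIV[-] women may mix vaccine-induced and natural antibody, with unknown size and direction

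*Combined protocol and SAP*

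**What the plan says.** The aim is "To quantify, and examine the determinants of, long-term antibody responses to, HPV vaccination" (Section VII.B). The first comparison in Section VII.B.1 is: "Geometric mean titers (GMT) and seropositivity (seroconversion) will be compared between 1) HPV-vaccinated WLWH and HPV-vaccinated HIV[-] women". Seropositivity is tested with Fisher's exact test. Logistic models then adjust for or assess a list of factors that names HPV genotype detection but not sexual behavior, and that ends in an open et cetera.

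Four other statements bear on how the result can be read:

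- Section VI.F.1.b: "the study nurse will collect one 5 mL tube of blood from all participants for HPV antibody serology testing". This is at enrollment. No pre-vaccination sample exists.
- Section VI.D.2, exclusion 6: "Report no previous sexual activity". All participants therefore report past sexual activity.
- Section VII.B.1, last paragraph, plans an analysis that begins "Among vaccinated and unvaccinated HPV seropositive WLWH". Antibody without vaccination is thus anticipated.
- Section VII.A.1 concedes "possible differences in sexual behaviors between Gardasil®-vaccinated WLWH vs. HIV[-] women" and for that reason builds a relative measure for Aim 1.

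Comparisons 2 and 4 of Section VII.B.1 set vaccinated against unvaccinated women within each HIV group. No comparison sets unvaccinated WLWH against unvaccinated HIV[-] women.

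**The concern.** Seroconversion means a change from negative to positive. With one late sample it cannot be observed, only seropositivity on that day. A woman whose vaccine antibody is absent or has waned still counts as positive if she has antibody from infection, and no cut-off is given to separate the two sources.

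The plan recognizes that exposure may differ between the two vaccinated groups and guards against this in Aim 1, but does not carry the guard into comparison 1 of Aim 2. Detection of HPV DNA shows current infection and misses cleared infection that left antibody behind. At stake is whether the study can say that WLWH keep vaccine antibody as often as HIV[-] women do.

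**Working it through.** **The plan's own figures.** Section VII.B.2 gives power for titers only: 274 per group for a 30% difference in GMT and 548 per group for 22%, both at 80% power. The standard deviation is not stated, so 274 cannot be reproduced independently. Solving back from 274 and a ratio of 0.70 gives SD = 0.357 / (2.80 × √(2/274)) = 1.49 ln units. With that SD, 548 per group detects a 22.3% reduction, so the two statements agree with each other. No power is given for seropositivity.

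**Inputs.** n = 548 per vaccinated group (Section VII.B.2); two-sided 0.05 (sidedness is my assumption). All seropositivity rates below are assumptions, because the documents give none.

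**Model.** Let v be the proportion with vaccine-induced antibody and q the proportion with natural antibody among women without vaccine antibody. Observed seropositivity is

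S = v + (1 − v)q.

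Power uses the two-proportion normal approximation, which runs slightly above Fisher's exact test.

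**A worked row.** With v = 90% (WLWH) and 95% (HIV[-]), and q = 30% and 20%:

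- WLWH: 0.90 + 0.10 × 0.30 = 0.930
- HIV[-]: 0.95 + 0.05 × 0.20 = 0.960
- SE under the null = √(0.945 × 0.055 × 2/548) = 0.01377
- SE under the alternative = √((0.930 × 0.070 + 0.960 × 0.040)/548) = 0.01374
- Power = Φ((0.030 − 1.96 × 0.01377)/0.01374) = Φ(0.22) = 0.59

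**Range** (natural rates are WLWH/HIV[-]):

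| Natural rates | Observed gap, true 90 vs 95 | Power | False rejection, true 95 vs 95 | False rejection, true 80 vs 80 |
|---|---|---|---|---|
| 0/0 | −5.0 points | 0.88 | 0.05 | 0.05 |
| 15/10 | −4.0 | 0.77 | 0.06 | 0.07 |
| 30/20 | −3.0 | 0.59 | 0.07 | 0.15 |
| 50/25 | −1.25 | 0.17 | 0.22 | 0.71 |

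To hide the 90 versus 95 gap completely, q in WLWH must reach 1 − 0.05(1 − q in HIV[-])/0.10. That is 50% if q is 0 in HIV[-] women and 57% if it is 15%. At equal true response the spurious difference is (1 − v)(q in WLWH − q in HIV[-]), so it is small when v is high.

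**Opposite direction.** If q is lower in WLWH, equal response shows a false deficit of the same size: at 80 versus 80 with q = 20/30, it is 0.20 × (0.20 − 0.30) = −2 points. For a real deficit, the ratio of seronegative fractions, WLWH to HIV[-], is multiplied by (1 − q in WLWH)/(1 − q in HIV[-]). It is overstated whenever q is lower in WLWH. On the difference scale the 90 versus 95 gap is widened only if q in HIV[-] women is more than twice that in WLWH, since 0.05q must exceed 0.10q.

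**Serology count.** Section VI.A gives at least 548 plus at least 108 controls in each HIV group, and a total of 1,302. But 2 × 548 + 2 × 108 = 1,312. The controls are also labelled HPV-vaccinated, although they are described as controls to the vaccinated groups.

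**The case against.** A reader might infer that comparison 1 is biased in favor of WLWH. The documents do not support that. Section VII.A.1 speaks only of "possible differences in sexual behaviors between Gardasil®-vaccinated WLWH vs. HIV[-] women", while Section VII.A.2 cites impaired immunity to HPV in WLWH, which could lower their natural antibody. The plan also allows for mother-to-child acquisition of HIV, in which HIV status is not a marker of sexual exposure. This objection stands: the direction is open.

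The assumed rates have no source. The nearest figure in the documents is 30% × 25% = 7.5% prevalence of vaccine-type infection (Section VII.A.2, a planning assumption for WLWH). That is current infection with any of four types, whereas serology is cumulative but covers only HPV16 and HPV18. Section I.C reports high seroconversion and four-year persistence in children living with HIV. If v is near 95%, false rejection is only 0.06 to 0.22 over the rates shown. This stands as a limit on size.

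The plan also does not stop at Fisher's test. Logistic models are planned, the covariate list is open, and sexual behavior is collected (Appendix III, part D). Comparisons 2 and 4 would reveal the background in each HIV group. This stands in part: the material to deal with the problem exists, but the plan does not commit to using it for comparison 1.

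Finally, Aim 2 is powered on GMT. A reader might extend the point to the whole of Aim 2, but no effect on the titer comparison has been shown.

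**Conclusion.** The point holds for seropositivity in comparison 1. The label seroconversion is wrong whatever the size of the bias, because one sample cannot show it. The contrast may mix vaccine-induced with natural antibody, and it is biased if natural seropositivity differs by HIV status. Even equal natural rates narrow a true difference: 15% in both groups takes 90 versus 95 from 5.0 to 4.25 points and power from 0.88 to 0.82.

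Size and direction are unknown. Under the assumed rates the loss of power for a real deficit runs from modest (0.77) to severe (0.17). A false difference at equal response is a minor matter at 95% vaccine seropositivity and a serious one only when that rate is lower and the natural rates are far apart. The documents support neither a statement that WLWH will look falsely better nor a statement that the GMT result is compromised.

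**What to change.** In Section VII.B.1:

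1. Delete the parenthetical word seroconversion and describe the endpoint as seropositivity at enrollment.
2. Add a comparison of unvaccinated WLWH with unvaccinated HIV[-] women for HPV16 and HPV18. It shows whether background seropositivity differs and in which direction.
3. In the logistic model for comparison 1, name lifetime partners and age at first sex as covariates alongside HPV16/18 detection.
4. As a sensitivity analysis only, report the seronegative fraction in vaccinated women divided by that in unvaccinated women, compared between WLWH and HIV[-] women as a ratio of ratios with its interval. State that it assumes the older, unvaccinated women carry the same natural background as the vaccinated women, and that it can over-correct. In simulation with 548 vaccinated and 108 unvaccinated per HIV group, equal true response of 80% and natural rates from 30/20 to 50/25, it gave a false deficit in WLWH in about 7% to 50% of studies when natural antibody in vaccinated women was a half to a quarter of the unvaccinated level.

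Do not make the conclusion depend on the raw and corrected results agreeing. Power could then not exceed that of the raw test: for 75 versus 85% that is 73%, 31% or 10% at natural rates of 30/20, 40/20 and 50/25.

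In Section VI.A, reconcile the vaccination status of the controls and the total of 1,302 against 1,312.

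The cost is wording and a little extra analysis. Plasma is already collected from all participants, so no new specimens are needed. The sensitivity estimate will have a wider interval.

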This study will recruit women attending collaborating clinics and women from the communities surrounding those clinics. Three groups will be recruited:

- 757 HPV-vaccinated WLWH (Group 1),
- 757 HPV-unvaccinated WLWH (Group 2), and
- 757 HIV[-] women who are HPV-vaccinated (Group 3)
- 757 HIV[-] women who are HPV-unvaccinated (Group 4)

Within the HPV-vaccinated groups 1 and 3, the study will recruit at least 274 women with three doses and 274 women with two doses, with the remaining 209 will not be selected by the number of doses and may have 2 or 3 doses. The number of doses of HPV vaccination a woman received is dictated by introduction of HPV vaccination in Rwanda as previously shown in **Table 1**. In general, most Rwandan women born in 2003 or later will have been vaccinated with two doses of Gardasil®, women born between 1996 and 2002 will have been vaccinated with three doses of Gardasil®, and women born in 1995 or earlier will be unvaccinated.

Table 3. Target population by HIV status and age

HIV Status	Approximate number of HPV vaccine doses	Birth year	Age at year of study enrollment (years)		N
			in 2021	in 2023	
WLWH	3 doses	1996-2002	19-25	21-26	274
	2 doses	2003-2005	16-18*	18-20	274
	2 or 3 doses	1996-2005	19-25	18-26	209
	0 doses - unvaccinated	1993-1995	26-30*	28-31*	757
HIV[-]	3 doses	1996-2002	19-25	21-26	274
	2 doses	2003-2005	16-18*	18-20	274
	2 or 3 doses	1996-2005	19-25	18-26	209
	0 doses- unvaccinated	1993-1995	26-30*	28-31*	757
TOTAL					3,028

*Only women age 18-28 are eligible for enrollment.

Therefore, we will recruit by age, which will serve as a useful and very good proxy for HPV vaccination status, which otherwise would be difficult to confirm in real time at enrollment. HPV vaccination status then will be confirmed by retrospective review of the HPV vaccination records kept by the Rwanda Ministry of Health (MoH), who are collaborating on this project. The number of women recruited will therefore be stratified by age (as proxy for vaccine status) and HIV status (**Table 3**).

VI.D. Eligibility Criteria

VI.D.1 Inclusion Criteria

1. Gender: Female
2. Age: 18-28 years. The age of inclusion criteria will likely be restricted as age-specific enrollment goals are met.
3. Physically and mentally able and willing to participate in the study.
4. Willing to provide written and signed or thumb printed, informed consent.

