Using the variance of GMT for HPV antibodies from Einstein et al. (111, 112), a sample size of at least 274 will provide 80% power ($p=0.05$) to detect a 30% difference in GMT between HPV-vaccinated WLWH and HIV[-] women for a given number of doses. If there is no appreciable difference in the titers between those who got 3 or two doses, we can combine those groups with different doses. In that case, with a sample size of at least 548, there will be 80% power ($p=0.05$) to detect a 22% difference between HPV-vaccinated WLWH and HIV[-] women.

VII.C. Exploratory Aim: A Study of 6-12 Month Type-Specific HPV Persistence

Given the size of the cohort of WLWH (n=1,514 at baseline), the planned follow-up of the HPV-positive WLWH, and the laboratory assay capacities that are available and will be

developed at the study lab, we have unique opportunity to look at determinants of early, short-term HPV genotype-specific persistence/clearance in young women. Studies of HPV persistence in WLWH, especially in SSA, are limited in number and size (113-120). There is a growing body of evidence that an altered CVM (cervicovaginal dysbiosis) is associated with persistent HPV infection (86) but there are no published data on its role in HPV persistence in WLWH. There is evidence of greater cervicovaginal microbiotic diversity in WLWH compared to HIV[-] women (121) and a complex, possible inter-dependence of CVM and HPV natural history (122). Given the importance of short-term HPV persistence as a biomarker of cervical-cancer risk (123) as well as an endpoint for prophylactic HPV vaccine trials, this is a unique opportunity to understand its determinants.

Paired baseline and follow up specimens from participants whose baseline cervicovaginal specimen tests HPV positive will have their cervicovaginal microbiome characterized. We will examine factors such as baseline and history (if available) of HIV disease status (HIV viral load and CD4), the presence of the HPV genotype at other anatomic sites, CVM composition, and other risk factors (e.g., sexual behaviors) on whether HPV infection persists vs. clears.

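### Aim 2's 22% detectable GMT difference hangs on an undefined look at dose differences; a dose-adjusted log-titre comparison makes that condition unnecessary and protects the HIV contrast if serology goes beyond the balanced 548 per group

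*Combined protocol and SAP*

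**What the plan says.** Section VII.B.2 makes two power statements for the HIV comparison among vaccinated women. Within one dose group, "a sample size of at least 274 will provide 80% power ($p=0.05$) to detect a 30% difference in GMT". For the doses together, "with a sample size of at least 548, there will be 80% power ($p=0.05$) to detect a 22% difference". The second follows from a condition: "If there is no appreciable difference in the titers between those who got 3 or two doses, we can combine those groups". No test, margin or threshold defines when the condition is met. The variance comes from a cited study, and its value is not given.

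Section VII.B.1 states that "Differences in GMT and seropositivity will be tested for statistical significance using the Mann-Whitney and Fisher's exact tests, respectively". The same section plans the HIV comparison both overall and by dose group, with no condition on the overall one. It also plans ANOVA models that list number of doses and HIV status among the factors. It does not say which analysis is the main one, whether titres are logged for the ANOVA, or which analysis the power figures belong to.

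Section VI.A fixes the minimum serology sample at 548 per vaccinated group, half with three doses and half with two, and allows testing of up to 3,028 samples. Section VI.C recruits 274 women per dose in each vaccinated group of 757; "the remaining 209 will not be selected by the number of doses and may have 2 or 3 doses".

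**The concern.** This is a test-then-pool rule. The better figure (22%) is offered only if the dose groups look alike, and nobody has to say in advance what alike means. The Executive Summary makes the move from three doses to two a study question, so a dose difference is a live possibility. If one appears, the power section falls back to 30%.

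The power statement is for a GMT difference, while the named test is a rank test that yields no GMT ratio. The adjusted analysis that would answer the question is listed but has no stated role.

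A second matter arises only if serology goes past the balanced minimum. If the dose mix then differs by HIV status, an unadjusted overall comparison carries part of the dose effect into the HIV effect.

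**Working it through.** **Inputs.** From the documents: 274 and 548 per group, 30% and 22%, 80% power, alpha 0.05 (Section VII.B.2); the 50:50 dose split and the ceiling of 3,028 samples (VI.A); 209 of 757 not selected by dose (VI.C). Assumed: a two-sided test, normal log titres, and three- to two-dose titre ratios r of 1 to 3. The documents give no r.

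**1. Reproduce the plan's figures.** The SD is not stated, so solve for it from the 274 / 30% statement, reading 30% as a reduction:

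SD = |ln 0.70| / [(1.960 + 0.842) × √(2/274)] = 0.3567 / 0.2394 = 1.490 on the ln scale.

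The statement is for a given number of doses, so this is a within-dose SD. At 548 per group the detectable log difference is 2.802 × 1.490 × √(2/548) = 0.2522, and 1 − exp(−0.2522) = 22.3%, against the stated 22%. Power for exactly 22% is 78.8%. Reading 30% as an increase gives SD 1.096 and 20.4% at 548, which does not match. The two stated figures therefore agree with each other as reductions; the SD itself cannot be checked.

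**2. Add a dose term.** With doses 50:50 in both HIV groups, dose and HIV status are uncorrelated. The residual SD stays at 1.490, so the detectable reduction at 548 stays at 22.3% and power for 22% at 78.8%, for any r.

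**3. Compare with the unadjusted pooled analysis.** Pooled SD = √(1.490² + 0.25 × (ln r)²). The Mann-Whitney column uses the asymptotic efficiency 3/π = 0.955.

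| r | Pooled SD | Detectable, t-test | Power for 22%, t-test | Power for 22%, Mann-Whitney |
|---|---|---|---|---|
| 1.0 | 1.490 | 22.3% | 78.8% | 76.9% |
| 1.5 | 1.504 | 22.5% | 78.1% | 76.2% |
| 2.0 | 1.530 | 22.8% | 76.7% | 74.8% |
| 3.0 | 1.588 | 23.6% | 73.6% | 71.6% |

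Adjustment gains 0 to 2 points over the unadjusted t-test for r up to 2. Mann-Whitney costs about 2 further points under log-normality. Simulation (4,000 runs per scenario) of Mann-Whitney against the adjusted model gave 76.6% vs 77.8% at r = 1, 76.1% vs 79.2% at r = 2, and 71.1% vs 77.4% at r = 3.

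**4. Bias in the balanced 548.** There is none. Simulated Mann-Whitney false rejection at r = 2 was 4.9%.

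**5. Bias if all 757 per group are tested.** The three-dose share can run from 274/757 = 36% to (274 + 209)/757 = 64%, so the largest possible difference between the HIV groups is 209/757 = 0.276. Spurious log GMT ratio b = 0.276 × ln r; SE = 1.490 × √(2/757) = 0.0766; false rejection = Φ(−1.96 − b/SE) + 1 − Φ(1.96 − b/SE).

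| r (assumed) | b at the bound | Spurious GMT ratio | False rejection at the bound | At half the imbalance |
|---|---|---|---|---|
| 1.5 | 0.112 | 1.12 | 31% | 11% |
| 2.0 | 0.191 | 1.21 | 70% | 24% |

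Adding the dose variance to the SE changes the bound to 30% and 68%. Simulated Mann-Whitney gave 30% and 68%, and the dose-adjusted model about 5% in both cases.

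**The case against.** The strongest reply is that the plan already contains the remedy. Section VII.B.1 has the dose-stratified comparison and an ANOVA listing number of doses alongside HIV status. A reader might infer from the Mann-Whitney sentence that only a crude test is planned; the documents do not support that. What remains is that neither analysis is named as the main HIV contrast or connected to the 22%.

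A reader might also infer that the overall comparison is abandoned if doses differ. Section VII.B.1 plans it without condition; the condition sits only in the power paragraph. That is right, and it means the two sections do not agree on when the combined comparison applies.

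Nor is the HIV comparison biased as designed. The sample behind the power statement is balanced by dose, and testing beyond it is optional. The 31% and 70% need full testing, every unselected woman three-dose in one HIV group and two-dose in the other, an assumed titre ratio, and reliance on the crude test alone. Table 3 gives these women the same birth years in both HIV groups, so the bound is not a forecast. Some imbalance is still plausible: Section I.A reports HIV prevalence of 1.8% at ages 20–24 and 3.8% at 25–29, and two-dose women are the youngest, so two-dose women with HIV may be harder to find.

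A rank test is defensible for titres, and its power cost is minor. That stands, and is why it can stay as a sensitivity analysis.

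**Conclusion.** The concern holds in a limited form. The 22% is conditional on an undefined, data-dependent judgement that the analysis does not need: with dose in the model and the planned split, about 22% is detectable at 548 per group whether or not doses differ. The gain in power is small. The gain in clarity is larger, since the power section otherwise supports only 30% when doses differ. Protection against dose-mix bias matters only beyond the balanced 548, where the rates above are upper bounds on assumed ratios.

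It would be too strong to say that adjustment delivers 22% unconditionally. The figure still rests on an SD from a cited source (1.49 is back-solved), on near-balanced doses, and on an HIV effect similar at both doses; otherwise it describes an average effect. Dose also follows birth year (Table 3), so the dose term absorbs age and time since vaccination and cannot be read as a pure dose effect.

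**What to change.** In Section VII.B.1, name as the main Aim 2 HIV comparison a linear model of log titre on HIV status and number of doses, using all vaccinated women tested. Report the GMT ratio with its 95% CI, and report the HIV-by-dose interaction. Keep a dose-stratified Mann-Whitney test as a sensitivity analysis.

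In Section VII.B.2, delete the condition on dose similarity, tie the 22% to this model, and state the SD and the direction of the difference (the figures match a reduction). Add a sentence noting that the dose term also carries birth-year differences.

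The cost is wording only: no extra women, samples or assays, and the adjustment is one the plan already lists.
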